11.5 Efficacy Analyses

11.5.1 Hypothesis Testing Strategy and Multiplicity Adjustments

The analysis for the primary efficacy endpoint will be performed at an alpha risk of 5% (two-sided). Statistical analysis of the key secondary efficacy endpoint will be performed only if the primary efficacy endpoint is significant.

11.5.2 AGE Events

An overview of all AGE events will be provided, including the number of subjects with AGE events, number of AGE events by severity (not available, mild, moderate, severe), number of AGE events per subject by count, number of AGE events by NoV GI genogroup and GII genogroup from first dose until the end of the primary observation period, summarized by trial arm and overall, in the FAS.

For confirmed NoV AGE events with derived onset date from first dose until end of the primary observation period, number of subjects with AGE events, number of AGE events GI positive, and GII positive, number of AGE events by severity (no severity score, mild, moderate, severe, mod/sev), number of AGE events per subjects, number of AGE events by norovirus genotype (genotype, pending, quantity not sufficient, or indeterminate), and without co-infection, with co-infection (each individual pathogen, multiple, any) will be summarized by trial arm and overall, in the FAS and in the PPS-E. This summary will be repeated in the FAS during the primary observation period for medically attended NoV AGEs. It will also be repeated for NoV AGEs from Dose 1 until the end of trial, for NoV AGEs from Dose 1 until Dose 2, and for NoV AGEs from 28 days post dose 2 until the end of the trial in the FAS.

For the first confirmed NoV AGE event with derived onset date in the primary observation period, AGE duration in days, number of days with loose/liquid stools, number of episodes of loose/liquid stools in a day, number of days with vomiting, number of episodes of vomiting in a day, health care provider visits (yes/no), hospitalization for AGE treatment (yes/no), oral rehydration needed (yes/no), subjects treated with IV hydration (yes/no), MVS, severity (not available, mild, moderate, severe) will be summarized descriptively overall and by trial arm using mFAS. This summary will be repeated for primary endpoint AGE events (GI.1 / GII.4 without co-pathogens) and for primary endpoint events in the PPS-E.

11.5.3 Primary Endpoint

The primary endpoint for the study is the time to first occurrence during the primary observation period (see Section **9.3.4**) of a mod/sev AGE event (see Section **ERROR! REFERENCE SOURCE NOT FOUND.**) associated only with GI.1 or GII.4 NoV genotypes (see Section **9.3.4**). Subjects without an AGE event will be censored at their last information date (see Section **9.3.6.1**). The time to event endpoint will be derived as per Section **9.3.8**. The analyses will be performed using the mFAS.

11.5.3.1 Primary Analysis

The primary analysis method will be a time-to-event stratified CPH model using Efron's method for handling ties. The model will include a term for randomized trial arm and will be stratified by country. In the event that model convergence is not achieved, countries with a smaller number of subjects contributing to the analysis will be pooled by region. The 95% CI for VE will be derived from the CI estimation of the hazard ratio obtained from the CPH model. Kaplan-Meier median time to event and plots will also be presented by trial arm. The primary efficacy objective is met if the lower bound of the 95% CI for the VE is above 0%.

To assess the proportional hazards assumption, the following will be examined as suggested by Therneau & Grambsch, 2000.

For each trial arm (x), a plot of log negative log survival function (i.e., log [-log S_0 (t|x_i)]) versus the log of survival times for each trial arm should produce roughly parallel lines if the hazards are proportional over time.

Analyses of the primary efficacy endpoint will not be adjusted based on these plots. A sensitivity analysis to assess the robustness of the primary analysis will be performed as described in section **11.5.3.3**.

11.5.3.2 Supplementary Analysis

The following supplementary analyses will be performed for the primary efficacy endpoint:

- Analysis based on the PPS-E using the same definition of the AGE events and same statistical methods as for the primary endpoint analysis as described in sections 11.5.3 and 11.5.3.1.
- Analysis of multiple moderate or severe events per subject will be performed using the Andersen-Gill extension of the Cox model (Andersen & Gill, 1982), stratified by country similarly to the primary endpoint. Recurrent AGE events are described in Section 9.3.2 The total number of events, the total time at risk (see Section 9.3.6.3) and unadjusted event rate (see Section 9.3.7) will be presented. Vaccine efficacy will be derived and presented in the same way as the primary analysis in Section 11.5.3.1.

11.5.3.3 Sensitivity Analysis

A sensitivity analyses of the primary efficacy endpoint will be performed by calculating the

VE as 1 - Incidence Rate Ratio

and corresponding CI based on Poisson distribution. The incidence rate ratio (IRR) is then defined as

 $(s_1 / T_1) / (s_0 / T_0)$

where

 s_1 = number of events in HIL-214 arm,

 s_0 = number of events in Placebo arm,

 T_1 = total person-time at risk in HIL-214 arm,

 T_0 = total person-time at risk in Placebo arm.

Wald confidence limits for the mean IRR will be derived using a Poisson regression model accounting for the log-transformed time at risk of the subject, adjusted for country.

11.5.4 Key Secondary Efficacy Endpoint

11.5.4.1 Vaccine Efficacy Associated with Any GI or GII Genotype

The key secondary efficacy endpoint for the study is the time to first occurrence during the primary observation period (see Section 9.2.6) of mod/sev AGE case (see Section ERROR! REFERENCE SOURCE NOT FOUND.) associated only with any GI or GII NoV genogroups (see Section 9.3.4). Subjects without an AGE event will be censored at their last information date (see Section 9.4.6.1). The time to event endpoint (months) will be derived as per Section 9.3.8 time to event The analysis will be performed on the mFAS and will follow the same analysis as in Section 11.5.3.1.

11.5.5 Secondary Efficacy Endpoints

The analysis of secondary vaccine efficacy endpoints as described in Section 9.0 will follow the primary analyses specified in Section 11.5.3.1. The secondary efficacy analyses will be performed on the mFAS.

11.5.5.1 Vaccine Efficacy caused by GI.1 or GII.4 Irrespective of Other GE Pathogens

The first secondary efficacy endpoint for the study is the time to first occurrence during the primary observation period (see Section 9.2.6) of moderate or severe AGE associated only with GI.1 or GII.4 NoV genotypes (see Section 9.3.4) irrespective of the presence of other GE Pathogens. Subjects without an AGE event will be censored at their last information date (see Section 9.3.6.1). The time to event endpoint will be derived as per Section 9.3.8.

11.5.5.2 Vaccine Efficacy Associated with Any GI or GII Genogroup Irrespective of Other GE Pathogens

The second secondary efficacy endpoint for the study is the time to first occurrence during the primary observation period (see Section 9.2.6) of moderate or severe AGE associated with any GI or GII NoV genogroups (see Section 9.3.4) irrespective of the presence of other GE Pathogens. Subjects without an AGE event will be censored at their last information date (see Section 9.3.6.1). The time to event endpoint will be derived as per Section 9.3.8.

11.6 Secondary Immunogenicity Endpoint

11.6.1 Immunogenicity of HIL-214

The secondary immunogenicity endpoints for the trial are pan-Ig and HGBA blocking antibody concentrations. These endpoints will be summarized as seroresponse rates (see Section **9.5.3**), GMCs and GMFRs (see Section **9.5.4**) for HBGA blocking antibody concentrations and for pan-Ig antibody concentrations collected at Visit 1(Day 1), Visit 2 (28 to 56 days post dose 1 - prior to dose 2) and Visit 3 (28 days post, and when the subjects reach the age of 1 year (Visit 4), 18 months (Visit 5) and 2 years (Visit 6) (see Section **9.2.5**). These estimates will be presented by trial arm separately for GI.1 and GII.4 NoV genotypes. Summaries of results for Visits 1 through Visit 4 will be included in the primary and secondary efficacy analysis. 18 months (Visit 5) and 2 years (Visit 6) results will be summarized at the end of trial.

The number of subjects with seroresponse, seroresponse rate and 95% CI on post-dosing visits will be presented. The two-sided exact 95% CI will be estimated using the Clopper-Pearson exact method (Clopper CJ & Pearson ES, 1934). For details of the derivations of GMC and GMFR, see section 9.5.3. Longitudinal plots and reverse cumulative distribution plots for concentrations will be presented by genotype and trial arm. The secondary immunogenicity analyses will be performed on the FAS and the PPS-I.

11.7 Exploratory

Page 27 of 44

Page 32 of 44

12.0 Safety

The safety analyses will be performed based on the SAF, unless otherwise specified. For the end-of-trial analysis, the overall summary of safety events, and summary of SAEs will be summarized for the complete trial (i.e., first dose through end of trial).

12.1 Adverse Events

Unsolicited adverse events will be coded according to the MedDRA version 24.1.

An overall summary of the number of patients with AEs after first dose of trial vaccine and number of events will be summarized, with line items for each of the following:

- Solicited local AEs
- Solicited systemic AEs
- Unsolicited AEs
- SAEs
- AEs leading to trial vaccine dose withdrawal
- AEs leading to withdrawal from the trial.

12.1.1 Solicited Adverse Events

The following summaries will be prepared for each trial arm and overall after each dose of trial vaccine and after any dose:

- The number and percentage of subjects experiencing solicited local and systemic AEs; overall and by severity
- The number and percentage of subjects experiencing local and systemic AEs, for each of 7 days after vaccination; overall and by severity
- The number and percentage of subjects experiencing solicited local and systemic AEs by day of onset
- The number and percentage of subjects experiencing solicited systemic AEs by relationship to vaccine as determined by the clinical investigator.

Only solicited AEs collected up to 7 days after dosing of vaccine will be summarized. Percentages will be based on the number of subjects who had at least one non-missing assessment for a given event.

Solicited safety data collected 30 min post-vaccination will be summarized separately.

12.1.2 Body Temperature

Body temperature measurements will be summarized for the seven days following each vaccination, by route of measurement and overall. The following categories will be used to report body temperature measurements: below 38°C, 38°C or higher (Fever), 38°C to less than 39°C, 39°C to less than 40°C, and 40°C or higher. The number and of subjects having at least one non-missing measurement will be used as the denominator to calculate percentages. Fever related to trial vaccine will also be presented using the same temperature categories, starting from 38°C or higher.

Body temperature measured 30 min post-vaccination will be summarized separately.

12.1.3 Unsolicited Adverse Events

The number and percentage of subjects experiencing any unsolicited AE (up to 28 days after each vaccine dose) will be summarized by trial arm, and by SOC and PT. Unsolicited AE summaries will include solicited AEs ongoing after 7 days post-vaccination. Percentages will be calculated based on the number of subjects in the SAF.

Unsolicited AEs will further be summarized by relationship to the trial vaccine or trial procedure. Subjects with multiple events coding to the same SOC or PT will be counted only once in that level, according to the most related event.

Unsolicited AEs will similarly be summarized by severity to the trial vaccine. Subjects with multiple events coding to the same SOC or PT will be counted only once in that level, according to the most severe event.

Unsolicited AEs after each vaccination will be summarized in the following 3 ways: 1) overall for Day 1 (day of vaccination) to 28 days after each vaccination, 2) with onset between Day 1 (day of vaccination) and Day 7 after each vaccination, and 3) with onset between Day 8 and Day 28 after each vaccination. Each group will be summarized after each vaccine dose, and any vaccine dose by trial arm and overall.

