### 10.1.2 Solicited Adverse Events

The occurrence of selected udicator of safety will be measured/collected for 7 days following administration of each dose of uvestigational vaccine (including the day of administration) and will be recorded on the Local and Systemic Reactions eCRF page as applicable and as listed in Table 10.a.

Any solicited local or systemic AEs observed as continuing on Day 8 following each trial vaccination will be recorded as an AE on the AE eCRF for follow-up. For these persistent/prolonged solicited AEs the end date will be captured on the AE eCRF to permit a separate analysis from the unsolicited AEs (see Section 10.4.2).

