## 10.4 Collection and Reporting Procedures

# 10.4.1 Collection and Reporting Adverse Events

All AEs, whether considered elated to the use of the trial vaccine or not, must be monitored by the investigator until symptoms poside and any abnormal laboratory values have returned to Baseline, or until there is a satisfactory explanation for the changes observed, or until death, in which case a full autopsy report should be supplied, if possible. All findings must be reported on the AE eCRF and on the SAE form\*, if necessary (see Section 10.4.4). All findings in subjects experiencing AEs must also be documented in the subject's source documents. Any unsolicited AE will be collected for 28 days after each dose of trial vaccine. The subject's LAR will use the eDiary memory aid to record unsolicited symptoms for reporting to the site. AEs leading to discontinuation (from the trial or from the vaccination regimen) are collected throughout the trial. Even if the subject is deemed ineligible to receive further doses of trial vaccine, all efforts should be made to continue the collection of safety data according to protocol.

The following information will be documented for each event:

- Reported term for the AE.
- Start and end date, duration.
- Serious (Y/N).

- Severity.
- Investigator's opinion of the causality (relationship) between the event and administration of trial vaccine (related or not related).
- Investigator's opinion of the causality (relationship) to trial procedure(s), including the details of the suspected procedure.
- Action taken with the trial vaccine.
- Outcome of event.

\*SAE reporting will be done by eCRF. If the eCRF system is unavailable, a paper sponsor SAE form/paper CRF should be completed and the event must be entered into the eCRF once access is restored.

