## 10.4.2 Collection and Reporting of Solicited Adverse Events

The occurrence of selected indicators of safety will be conected on eDiary by the subject's LAR for 7 days following administration of each trial vaccine dose (including the day of administration) and will be recorded on the Locat and Systemic AEs eCRF, as applicable. These will be summarized in the final clinical study report under the category solicited AEs to differentiate them from unsolicited AEs. Any solicited local (injection site) or systemic AE observed as continuing on Day 8 following each trial vaccination will be additionally recorded as an AE on the AE eCRF for follow-up For these persistent/prolonged solicited AEs, the end date will be captured on the AE eCRF to permit a separate analysis from the unsolicited AEs.

Any solicited AE that meets any of the following criteria must be entered as an AE on the AE eCRF page.

- Solicited local (injection since eactions or systemic AEs that lead the subject to withdraw from the trial.
- Solicited local (injection site) reactions or systemic AEs that lead to the subject being withdrawn from the trial by the investigator.
- Solicited local (injection site) reactions and systemic AEs that otherwise meet the definition of an SAE (see Section 10.1.2).

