6.1 Changes from Protocol

A calendar day instead of any 24-hour period will be used to determine the timing of symptoms for acute gastroenteritis (AGE) events.

Antibody titer for both pan-Ig and HBGA will be reported as a concentration using the units AU/mL.

Subjects will be excluded from the immunogenicity per-protocol set if not in Modified Full Analysis and baseline blood sample not collected.

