9.4 Safety

9.4.1 Adverse Events After Vaccine Doses

Unsolicited AEs will be summarized up to 28 days after each vaccine dose if:

 $1 \leq AE Start Date - Date of Vaccine Dose + 1 \leq 28$

Unsolicited adverse events starting after 28 days after the first dose of vaccine but before the second dose, or starting 28 days after second dose, will not be included in the safety summaries, but will be included in the listings.

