9.4.2 Solicited Adverse Events

Solicited local AEs include Injection Site Pain, Erythema, Induration and Swelling, and solicited systemic AEs include Fever, Drowsiness, Irritability/Fussiness, Loss of Appetite, Vomiting and Diarrhea. Solicited AEs are collected at 30 minutes after vaccine dose and daily for 7 days starting on the day of vaccine dose.

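### Solicited reactions lasting past Day 7 are pooled into the unsolicited AE totals; the separate analysis that the protocol had in view appears in no visible SAP table, and SAP 6.1 does not list the change

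*SAP*

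**What the plan says.** **Protocol.** Section 10.1.2 says of a solicited AE still present on Day 8 that "the end date will be captured on the AE eCRF to permit a separate analysis from the unsolicited AEs". Section 10.4.2 repeats this purpose and says that such an event "will be additionally recorded as an AE on the AE eCRF". Section 10.4.1 lists, among the items recorded for each event, "Start and end date, duration". Section 10.2 treats solicited local AEs as related by default; the investigator judges the systemic ones. Section 13.1.5 describes the unsolicited AE tables without mentioning prolonged solicited events. For solicited AEs it promises a summary of the number of days on which each event was reported.

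**SAP.** Section 12.1.3 says: "Unsolicited AE summaries will include solicited AEs ongoing after 7 days post-vaccination". It also plans unsolicited tables by relationship, and for three onset windows (Day 1-28, Day 1-7 and Day 8-28) after each dose and after any dose. Section 9.4.1 assigns events to the 28-day window by AE start date. Section 12.1.1 limits the solicited tables to the first 7 days, and its four listed summaries include no number-of-days summary. Section 6.1 declares three changes from the protocol. The first begins "A calendar day instead of any 24-hour period will be used"; the other two concern concentration units and the PPS-I. None concerns AEs.

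**Denominators.** SAP 12.1.3, 12.1.4 and 12.1.6 plan summaries by dose. Sections 12.1.3 and 12.1.4 take percentages over the SAF, and so does 12.1.6. SAP 9.1.1 admits to the SAF anyone who received at least one dose, and SAP 11.3.1 plans to count subjects who received only one.

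**The concern.** A reader of the any-unsolicited and related-unsolicited lines expects new events that the diary did not solicit. Under SAP 12.1.3 those lines also contain reactions that began in the solicited window and had not resolved by Day 8. The vaccine is aluminum-adjuvanted and the placebo is saline, so persistence could plausibly differ by arm. If it does, part of any arm difference in these totals is prolonged reactogenicity, and the planned tables do not let a reader remove it cleanly. The related total is the more exposed of the two, because every prolonged local reaction enters it automatically.

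The after-dose-2 percentages raise a separate issue: children who never received dose 2 cannot have an event after it, yet they count in the denominator.

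**Working it through.** The plan gives no figure to reproduce, so the main check sets the passages side by side. All rates below are assumptions.

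**1. Is there a separate analysis?** The protocol states the purpose in two places (10.1.2 and 10.4.2). SAP 12.1.1 stops at Day 7. The overview in SAP 12.1 has six lines, none for prolonged reactions. SAP 12.1.3 places them with the unsolicited events. No visible SAP table isolates them.

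**2. Which tables are mixed?** SAP 9.4.2 names 4 local terms and 6 systemic terms ("solicited systemic AEs include Fever, Drowsiness, Irritability/Fussiness, Loss of Appetite, Vomiting and Diarrhea"), 10 in all.
- *Day 1-28 table:* mixed. Local terms sit on recognisable injection-site rows. A systemic term cannot be told from a new event with the same preferred term.
- *Onset tables:* "Unsolicited AEs will be summarized up to 28 days after each vaccine dose if" the start date lies within Day 1 to Day 28. With original onset kept, a continuing reaction falls in the Day 1-7 table and the Day 8-28 table is free of it. If Day 8 were entered as the start, it would fall in the Day 8-28 table. Neither document states the rule explicitly.
- *Totals:* subtracting one onset table from the overall table does not recover the total without these reactions, because one child can be counted in both windows.

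**3. Illustrative size.** Let *b* be the proportion with a genuine unsolicited AE, and *p* the proportion with a solicited AE continuing past Day 7, assumed independent. The reported proportion is 1 - (1 - b)(1 - p), so the arm difference added is (1 - b)(pV - pC), where V is vaccine and C is placebo. For related events, *p* is multiplied by the share *s* of persistent events that are local. The planned arm size is 1500.

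| Total | Assumed base | Persistence 2% vs 1% | Persistence 5% vs 1% |
|---|---|---|---|
| Any unsolicited | 20% | 21.6% vs 20.8%: 0.8 points, 12 per 1500 | 24.0% vs 20.8%: 3.2 points |
| Any unsolicited | 40% | 41.2% vs 40.6%: 0.6 points, 9 per 1500 | 43.0% vs 40.6%: 2.4 points |
| Related | 1%, s = 1 | 2.98% vs 1.99%: 0.99 points, 14.9 per 1500 | 0.99 x 4 = 3.96 points |
| Related | 5%, s = 0.5 | 0.95 x 0.5 x 1 = 0.475 points, 7.1 per 1500 | 0.95 x 0.5 x 4 = 1.90 points |

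Equal persistence in the two arms adds 0.

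**4. Number of days.** Protocol 13.1.5 says this summary will be provided; it is not among the four summaries in SAP 12.1.1. This gap is separate from the pooling. A count limited to the 7 diary days would not show what happens after Day 7.

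**5. Denominator.** If a share *m* of the SAF did not receive dose 2, the reported after-dose-2 rate is the true rate times (1 - m). For an assumed 2% rate:
- m = 1%: 2% x 0.99 = 1.98%
- m = 5%: 2% x 0.95 = 1.90%
- m = 10%: 2% x 0.90 = 1.80%

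The arm ratio is unchanged if *m* is equal in both arms. With m = 10% in the vaccine arm and 5% in the placebo arm it is multiplied by 0.90/0.95 = 0.947.

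**The case against.** **The protocol does not order a table.** Its wording enables a separate analysis; it neither mandates one nor forbids counting these events as unsolicited. Protocol 13.1 leaves analysis detail to the SAP, and SAP 12.1.3 states its rule openly. This stands. A reader might infer that the SAP reverses a protocol instruction, but the documents do not support that. What remains is a stated purpose that no visible table serves and that SAP 6.1 does not mention.

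**The onset windows already separate these events.** This largely stands for one table. An event described as continuing, with its start date, end date and duration recorded, most naturally keeps its original onset, which leaves the Day 8-28 table clean. Rows for solicited terms in the Day 1-7 unsolicited table would then be mainly persistent reactions. The overall Day 1-28 totals stay mixed, and SAP 12.1.3 does not say whether the relationship tables are split by onset window.

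**Persistence can be gauged elsewhere.** The day-by-day tables in SAP 12.1.1 give Day 7 prevalence, which roughly bounds what can continue to Day 8, apart from missing diary days. They do not show what did continue or for how long.

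**Double counting in the overview.** SAP 12.1 says: "An overall summary of the number of patients with AEs after first dose of trial vaccine and number of events will be summarized". A reader might infer that one reaction inflates this table by counting as both solicited and unsolicited. The documents do not support that as a fault: they do not say that the 12.1.3 rule governs the overview, no combined total is planned, and SAEs and withdrawal AEs overlap other lines by design.

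**The sizes are assumed.** This stands. Independence, the base rates and the local share are all assumptions. Systemic events rated related would raise the related figures and a local share below 50% would lower them, so the range is not a bound.

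**The SAF denominator may be meant per dose.** That is possible, but the text does not say so.

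**Conclusion.** The point holds as an undeclared and unserved purpose in the safety plan, not as a breach of a protocol rule. The Day 1-28 any-unsolicited and related totals will mix prolonged solicited reactions with new events. The Day 8-28 onset table is unaffected if original onset is the start date, which is the natural reading but is not written down.

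The true size is unknown. For each assumed 1-point arm difference in persistence, the any-unsolicited difference moves by 0.6-0.8 points (bases 40% to 20%) and the related difference by about 0.5-1.0 points (bases 5% to 1%, local share 50% to 100%). If persistence is equal in the two arms, the differences do not move.

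The missing number-of-days summary is a plain omission against Protocol 13.1.5. Read as written, the denominator rule understates after-dose-2 rates by the share without dose 2; it distorts the arm comparison only if that share differs by arm.

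All of this concerns descriptive safety tables. No test, decision rule or primary objective is touched. It should be fixed, but it is not critical.

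**What to change.** 1. **SAP 12.1.3:** add a table of solicited AEs continuing on Day 8, by arm, dose and term, with duration. Show the Day 1-28 any-unsolicited and related totals with and without these events.
2. **SAP 9.4.1 or 12.1.3:** confirm that the original onset date is the start date for a continuing reaction.
3. **SAP 6.1:** declare the convention as a change from the protocol.
4. **SAP 12.1.1:** add the number-of-days summary stated in Protocol 13.1.5.
5. **SAP 12.1.3, 12.1.4 and 12.1.6:** for after-dose-2 percentages, use the SAF subjects who received that dose.

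The cost is SAP wording and one or two extra tables. The protocol already has start date, end date and duration recorded for each AE, and SAP 11.3.1 already counts subjects with one or both doses, so no new data are needed.

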9.1 Analysis Sets

9.1.1 Safety Analysis Set (SAF)

The SAF will consist of all subjects who are randomized and received at least one dose of HIL-214 or placebo. Subjects will be analyzed according to the trial vaccine which they actually received.

Data from subjects who received one dose of HIL-214 and one dose of placebo will be analyzed in the HIL-214 group for summaries after corresponding HIL-214 dose and summaries after any dose, and in placebo group for summaries after the dose of placebo.

A subject may be excluded from the SAF due to major Good Clinical Practice violations.

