12.1.4 Deaths and Serious Adverse Events

SAEs and fatal SAEs occurring after each dose and after any dose will be summarized by vaccine dose and overall, by SOC and PT. Summaries will be provided by trial arm and overall. Percentages will be calculated based on the number of subjects in the SAF.

SAEs including fatal SAEs will be included in a subject listing.

SAEs and fatal SAEs will similarly be summarized by relationship and by severity as described for unsolicited events above.

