12.1.6 Adverse Events Leading to Withdrawal from Trial

Adverse events leading to withdrawal from trial occurring after each dose and after any dose will be summarized by vaccine dose and overall, by SOC and PT. Summaries will be provided by trial arm and overall. Percentages will be calculated based on the number of subjects in the SAF.

The adverse events will be listed.

Adverse events leading to withdrawal from the trial will similarly be summarized by relationship and by severity as described for unsolicited events above.

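### Post-dose-2 percentages for unsolicited AEs, SAEs and AEs leading to trial withdrawal are divided by the whole SAF, so they are understated by each arm's share of children who never received dose 2

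*SAP*

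**What the plan says.** - **Who is in the SAF (SAP 9.1.1).** "The SAF will consist of all subjects who are randomized and received at least one dose of HIL-214 or placebo". A child who stopped after dose 1 is included.
- **SAEs (SAP 12.1.4).** "SAEs and fatal SAEs occurring after each dose and after any dose will be summarized by vaccine dose and overall, by SOC and PT". The same paragraph then sets the SAF as the basis for percentages.
- **AEs leading to trial withdrawal (SAP 12.1.6).** "Adverse events leading to withdrawal from trial occurring after each dose and after any dose will be summarized by vaccine dose and overall". The SAF basis again follows in the same paragraph.
- **Unsolicited AEs (SAP 12.1.3).** The opening paragraph ends with "Percentages will be calculated based on the number of subjects in the SAF". The last paragraph orders the per-dose tables: "Each group will be summarized after each vaccine dose, and any vaccine dose by trial arm and overall". It gives no other denominator.
- **Where a narrower denominator is set.** For solicited AEs (SAP 12.1.1) and body temperature (SAP 12.1.2), percentages use subjects with a non-missing assessment or measurement.
- **Counts by dose (SAP 11.3.1).** The numbers of SAF subjects with one dose and with both doses are reported by arm.

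Nothing visible in either document limits a post-dose-2 denominator to dose-2 recipients.

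**The concern.** A child who never received dose 2 cannot contribute to the numerator of a post-dose-2 table. If that child stays in the denominator, the table treats a child who was not at risk as one who was at risk and had no event.

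The plan expects such children. It separates the FAS (one dose or more) from the mFAS (two doses), protocol 7.5 lists reasons for stopping vaccination while staying in the trial, and SAP 11.3.1 counts one-dose recipients.

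Two readings of the safety tables are at stake. The first is the level of risk after the second dose, which comes out too low in both arms. The second is whether events become more or less frequent from dose 1 to dose 2: the dose-1 figure is right and the dose-2 figure is diluted, so the comparison leans towards a fall.

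**Working it through.** The documents state no AE rate, no SAE rate and no share of children without dose 2, so there is no figure of the plan's own to reproduce. The planned arm size of 1500 is from SAP 8.0. Every rate below is an assumption, used to show the range.

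**Formula.** Let *d* be the share of an arm's SAF that never receives dose 2, and *p* the share of dose-2 recipients with an event. With *N* children in the SAF, dose-2 recipients number *N*(1 − *d*) and children with events number *pN*(1 − *d*).

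- SAF denominator: *pN*(1 − *d*) / *N* = *p*(1 − *d*).
- Dose-2 recipients as denominator: *pN*(1 − *d*) / [*N*(1 − *d*)] = *p*.

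The relative understatement is exactly *d*.

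**Within one arm**

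| True rate *p* | Share without dose 2, *d* | Shown on the SAF |
|---|---|---|
| 30.0% | 2% | 0.30 × 0.98 = 29.4% |
| 30.0% | 5% | 0.30 × 0.95 = 28.5% |
| 30.0% | 10% | 0.30 × 0.90 = 27.0% |
| 1.00% | 5% | 0.01 × 0.95 = 0.95% |

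In counts, with *N* = 1500, *d* = 5% and *p* = 20%: 1425 children receive dose 2 and 285 of them have an event. The table shows 285/1500 = 19.0%. Among those dosed it is 285/1425 = 20.0%.

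**Dose 1 against dose 2.** Suppose the rate is 30% after each dose and *d* = 5%. The dose-1 table shows 30.0% and the dose-2 table 28.5%. The apparent fall of 1.5 points comes from the denominator alone.

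**Between arms.** The displayed risk ratio is the true ratio × (1 − *d*, vaccine) / (1 − *d*, placebo).

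- Equal *d*: the factor is 1 and the ratio is unchanged.
- True 20% in both arms, *d* of 5% (vaccine) and 3% (placebo): 19.0% v 19.4%, ratio 0.95/0.97 = 0.979.
- True 20% in both arms, *d* of 5% (vaccine) and 10% (placebo): 19.0% v 18.0%, ratio 0.95/0.90 = 1.056.

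The direction depends on which arm loses more children before dose 2. The 20% to 30% in SAP 8.1 covers drop-out and non-evaluable samples together, so it is not an estimate of *d*.

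**The case against.** **The denominator in SAP 12.1.3 is partly inferred.** The SAF sentence closes the paragraph on the overall unsolicited AE summary, and the per-dose tables come three paragraphs later with no denominator of their own. This is fair, and it makes 12.1.4 and 12.1.6 the firmer evidence, since there the SAF basis follows the per-dose wording in the same paragraph. The SAF remains the plain reading of 12.1.3, as no other basis is given.

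**Little depends on these tables.** Safety is descriptive, counts are shown beside percentages, and SAP 11.3.1 lets a reader recompute the overall post-dose-2 figures. For rare SAEs the change is very small. All of this stands and limits the weight of the point. It does not make the stated denominator right.

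**A reader might infer a bias in favour of the vaccine.** The documents do not support that. They give no sign that the arms will differ in stopping, and the only reactions that protocol 7.5 names as ruling out dose 2 are anaphylaxis and severe hypersensitivity. Changing the denominator would not fully remove such a bias either: children who go on to dose 2 are a subset selected after randomisation.

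**A reader might infer a mismatch for children given one dose of each product.** SAP 9.1.1 analyses their data "in the HIL-214 group for summaries after corresponding HIL-214 dose and summaries after any dose, and in placebo group for summaries after the dose of" the control product. It does not say that such a child moves in the numerator but not in the denominator, and the natural reading is that both move.

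**The solicited tables differ for a reason.** Their denominator reflects diary fields that can be blank. The two kinds of table would rest on different bases even after the change, so the contrast is not itself an error. It does show that the SAP names a narrower denominator where it wants one.

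**Conclusion.** The point holds in a limited form. As written, post-dose-2 percentages for SAEs and AEs leading to trial withdrawal, and for unsolicited AEs on the plain reading, show *p*(1 − *d*) instead of *p*. The understatement equals each arm's share without dose 2. For an assumed 2% to 10%, it is 0.6 to 3.0 points on a true 30%; for an SAE rate of 1.00%, it is 0.05 points at 5%. Dose-1 versus dose-2 comparisons are distorted even when stopping is equal between arms. The arm comparison is affected only if stopping is unequal, and nothing in the documents says that it will be.

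Post-dose-1 and any-dose tables are right on the SAF, because every SAF subject received at least one dose. SAP 12.1.5 concerns dose withdrawal after the first dose and needs no change. Solicited AEs and body temperature are outside the point. Because the tables are descriptive and the share missing dose 2 may be small, this is a correction worth making before the tables are programmed, not a threat to the trial's conclusions.

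**What to change.** Add to SAP 12.1.3, 12.1.4 and 12.1.6:

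> For summaries after a given dose, percentages are based on SAF subjects who received that dose, by the product received at that dose; for summaries after any dose, on all SAF subjects.

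This stays within the SAF, so it agrees with the protocol's rule that safety summaries use that set. It also makes explicit the basis for children who received both products.

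The cost is one sentence and a denominator change in the table programs. The dose-2 counts by arm are already planned in SAP 11.3.1. Post-dose-2 percentages become slightly higher, and they describe children who continued dosing, so they should be read alongside the any-dose tables.
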